Power and Sample Size Estimates. A within-subject design is used to evaluate the physician intervention and a randomized control trial is used to evaluate the patient intervention. However, the outcomes of both interventions will be modeled at the patient level in a single model. We used the person-level multi-site/block trial design within Optimal Design to conduct power analyses because the unit of analysis is the patient-physician visit and data from these visits will likely be more similar within physicians than between physicians. The first power analysis is based 216 patients not lost to attrition, who should be eligible for clinical trials and thus randomized into the patient-level intervention. (See Participants and Recruitment—p. 7) We define the *primary outcome* of our study as patients' decisions to enroll in clinical trials, where a "success" is defined as a patient deciding to enroll. Our primary objective (Aim 1) is to examine the extent to which patient- and physician-level interventions affect physician and patient trial-related decisions, and thus we seek a sample size that gives us sufficient power to detect both the main effect of intervention and important interaction effects. We chose GEE power analysis for nested binomial outcomes with within-cluster treatments⁶⁶ as the best available model to estimate power for our primary objective; such estimates are lacking for HLM models. With 24 physicians and 9 patients per physician (i.e., 216 patients), a Type I error rate (α) of .05, and ICC of .05, and probability of success under the null hypotheses (p_{H_0}) of .25, we are well powered to detect p_H of .35 ($b = 0.48$, odds-ratio = 1.61) with power > .99. Our secondary objective, (i.e., Aim 2) is to examine whether patient race influences the effectiveness of either patient- or physician-level interventions on our primary outcome, and we remain well

powered to detect 2-way and 3-way interactions. We will also examine effects of the interventions, and between-race differences in effects of the interventions on other binary or continuous outcomes (e.g., trial offers, patients' perceptions of patient-centeredness, perceived involvement in care, trust in physician, etc.). The power analysis described above holds for the binary outcomes. For the continuous outcomes, we used block person-randomized trial module in Optimal Design⁶⁷ to estimate power. Considering each of the 24 physicians as "blocks" and assuming about 9 patients per physician, a Type I error rate (α) of .05, between-physicians variability in effect size (σ_{β}^2) of .05, 5% of variance in outcomes due to physicians and a medium effect size (d) of .50, power to find effects exceeds .90. Our final objective, (Aim 3) is to explore the extent to which patient-physician communication mediates the effects of the interventions on the outcomes. We will use Multi-level Structural Equation Modeling (MSEM) that control for patient-physician nesting to fit path analyses. The specific structure (i.e. direct and indirect paths of the models) will be guided by results from analyses conducted for our first and second aims. We therefore consider the MSEM exploratory in that we are the first researchers to examine these effects in this context. Thus, at this point we lack the specification of the model parameters needed to provide accurate estimates of power for this exploratory aim.

We will use Multi-Level Models (MLMs) that include separate variables identifying both interventions, as well as a variable indicating the interaction between the two phases. This model allows us to examine the main effect of each intervention, and multiplicative effects of having been exposed to both interventions. For purposes of clarity, we discuss hypotheses for each intervention separately, but as already noted, they will be tested in the same MLMs. We will model most outcomes (specifically, patients' perceptions of patient-centeredness, perceived involvement in care, trust in physician, and team perceptions; patient active participation, and physician patient centeredness, patient understanding of informed consent) as continuous variables. We will use binomial logistic models for binary outcomes (e.g., trial offer) and multinomial logistic regression for categorical outcomes (e.g., patients' self-reported participation decision - "yes", "no", "undecided"). We will also explore whether a single model best captures the meditational processes for both Black and White patients or separate models are needed.

Models for Aim 1: As we have described the objectives and outcomes above, here we generally describe the models that will be used to test support for our hypotheses. All outcomes, and coefficients for each of the intervention effects and interactions between them, will be modeled at the patient level of the model (level-1); that is, they will be nested within physicians (level-2). We will use one MLM for each outcome to test the three Aim 1 hypotheses. We use this particular approach to examine the interventions' effects because it is believed that the two interventions will not only work independently, but also interactively. Thus, we use a model that simultaneously controls for the main and interactive effects of both interventions as we examine their unique contributions.

Control variables: At the patient level of the model, we will control for factors such as decisional control preferences, relevant attitudes, health literacy, number of boosters received, disease severity, co-morbidities, whether there is an available clinical trial for the patient, and if so, characteristics of the trial (e.g., difficulty, complexity). At the physician level, we will control for relevant racial and professional attitudes, and decisional control preferences. Because the physician-focused phase involves a quasi-experimental design, we will also control factors that might threaten the internal validity of the intervention, such as time since study has begun, and number of previous interactions between patients and physicians.

Hypothesis 1a. Outcomes will be significantly improved in the patient intervention group, relative to the usual care group. To test hypothesis 1a, we will fit separate MLMs to examine continuous and binary outcomes assessed during or after each visit in which a trial was discussed. The focal independent variable will be the dummy-coded variable indicating whether the patient was in the usual care or intervention group. Support for hypothesis 1a will be indicated by a significant coefficient for this independent variable (i.e. intervention/usual care).

Hypothesis 1b. Outcomes will be significantly improved for patients after the physician intervention, as compared to outcomes before the physician intervention. The focal independent variable is the dummy-coded variable indicating whether or not the patient's physician has received the physician intervention at the time of the clinic visit. Note that this variable is a within-subject variable among the physicians; however, because we theorize that the patient-physician communication quality is central to offers and acceptance of clinical trials, this variable is introduced in the model at level-1 (patients). Support for hypothesis 1b will be indicated by a significant physician-intervention coefficient (i.e., pre/post physician intervention).

Hypothesis 1c. The combined effects of the two interventions will be multiplicative, rather than simply additive. The focal independent variable is the dummy coded variable for the product interaction term in the model. We expect the physician intervention to be more effective among patients who received the patient intervention; we expect a statistically significant positive coefficient for the interaction term.

Models for Aim 2: Hypothesis 2 (African American – White Differences) - Effects of the intervention will be significantly greater among African American than White men. We will test the hypothesis by introducing 2-way interactions between race and patient- and physician-focused interventions, and a 3-way race by patient-focused by physician-focused intervention variable, to the models. A significant coefficient for the 2-way interaction between race and the patient-focused intervention, will indicate whether the magnitude of the intervention is influenced by patients' race. The coefficient for the 3-way interaction will be used to assess whether the magnitude of the interactive effect of the patient- and physician-focused interventions depends on patients' race. We will probe the specific nature of these interactions with methods outlined by Preacher, et al.¹⁶⁹ We will also explore the moderating effects of other patient level variables (e.g., socio-demographics, race-related attitudes, etc.) in separate analyses.

Models for Aim 3: Hypothesis 3 (Mediating effects of patient-physician communication): The quality of patient-physician communication will mediate the effect of the interventions on trial offers, and, in turn, on patient understanding of trials offered and decisions to participate. We will use Multilevel Structural Equation Modeling (MSEM) to assess mediational/indirect effects. We will examine the specific relationships (paths) specified within the models as well as how well the overall model fits the data; we will use standard indices of the quality of fit (e.g. RMSEA, CFI). We will utilize observational measures of communication quality and relevant patient's perceptions of the interaction (see measures above) as measures of the mediating variables of the interest in the model. Separate models will be used for each outcome. Separate models will be conducted for separate outcomes.

References

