The first intervention is a randomized controlled trial focused on patients. This intervention is broken into two separate but identical parts, in which half of the patient sample participates before the physician intervention, and the other half participates after the physician intervention. In the first part, patients of participating physicians will be recruited and tracked until they become eligible for a trial, at which time they will be randomized into an intervention or usual care group. They will continue their participation until: they receive a trial offer, or they have four interactions with their physician without receiving an offer. Regardless of the number of interactions, this group of patients will discontinue their active participation when the physician intervention begins. Thus, these patients will participate for a maximum of 20 months. In the second part, which occurs after the physician intervention has been conducted, the remaining half of the patient sample will be recruited and tracked, and eligible patients will be randomly assigned to the two groups. Again, their participation will continue until they receive a trial offer, they have four interactions with their physician without an offer, or data collection ends. These patients will, thus, also participate for a maximum of 20 months. We will utilize a block-randomized design in which physicians are treated as blocks and patients are randomized to a group.

The second intervention is a within-subjects interrupted time series quasi-experiment focused on physicians.³⁰ Physicians will be recruited at the beginning of data collection, prior to any patient recruitment (i.e., once IRB approval has been received—approximately nine months after the formal start date of this grant award). In this within-subjects design, physicians provide pre-intervention data for 20 months, then receive the intervention and continue their participation for another 20 months (i.e., until the end of data collection). The same physicians will remain in the study throughout data collection; thus they will provide both pre intervention and post intervention data that will be used to examine the effectiveness of the physician-focused intervention.

Figure 2: Study Design and Procedures Overview

Patient Procedures, Measures, and Intervention

Patient Procedures.

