Time 2: Pre- and Post-Clinic Visit: On the day of a clinic visit (for those patients who have been prescreened and found to be potentially eligible for an available clinical trial), clinic/research staff will meet with patients to remind them that the visit will be video recorded and to provide a copy of the patient intervention booklet, if needed. Just prior to and following the visit, patients will complete brief questionnaires (See Appendices H and I: Time 2 pre- and post questionnaires). If family members or companions are present, they will be told about the study and asked for consent (See Appendix C: Companion Information Sheet). Similarly, clinical staff who will be in the room during video recording will be provided an information sheet (See Appendix D: Health Care Provider Information Sheet.) Patients will receive a \$10.00 gift card following this visit. Also, patients will be asked whether they were offered a clinical trial; if they were not, they will be told that they are still in the study and may be contacted again in the future. They will continue to be tracked for up to a total of 4 visits or until the end of their participation. If they still receive no offer after a fourth visit, they will no longer be tracked. If they are offered a trial, they will proceed to Time 3.

Time 3: Follow-Up Interview: A week after the visit, research staff will contact patients (on the phone or in person as convenient to patients) who were offered a trial to conduct a brief interview (Appendix J: Time 3 Follow-Up Interview). This interview should take approximately 20 minutes. Patients will receive a third \$10.00 gift card at the end of this interview.

Time 4: Medical Record Review: Research staff will examine patient medical records to determine participating patients' disease status, co-morbidities, whether and when they were eligible for an available trial, whether they completed procedures for trial enrollment and/or enrolled in a trial, and trial characteristics (e.g., difficulty, complexity) that may affect physicians' decisions to offer a trial and/or patients' decisions to participate.

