Observational Measures. Trained raters will observe and rate video recorded visits. These individuals will have completed all requirements of the IRB (e.g., CITI training, added as key personnel if required). We will follow procedures used in our prior studies to train raters and ensure acceptable inter-rater reliability. Raters will determine whether a trial was discussed and/or offered and assess the quality of trial-related communication, following procedures in our prior research,⁶⁴ physician patient-centeredness,⁴⁷ and patient active participation in the interaction.⁴⁷

Process Evaluations. Treatment fidelity and participant satisfaction will be assessed using audio and video recordings of the intervention procedures to monitor and assess these processes.

STATISTICAL ANALYSES

Qualitative Analyses of Follow-up Interviews. Audio-recordings/transcripts of follow-up interviews will be analyzed using directed content analysis methods. Directed content analysis is useful when researchers have specific categories in mind based on a priori or existing theory.⁶⁵ Using an iterative process, a team of coders, trained and supervised by [name], will listen to the recordings and then develop, refine, and apply a coding system for analyzing patients' perspectives on factors that affected their participation decisions. This aspect of the research is exploratory; findings from this analysis will not be directly integrated into the quantitative analyses and are not directly related to the aims.

Quantitative Data Preparation. Prior to any hypothesis testing we will examine multi-item measures to ensure that total scores and any factors derived from these items have acceptable internal consistency (e.g., Cronbach's α), produce meaningful total scores, and yield distributions appropriate for planned analyses. If there are departures from normal distributions or unequal variances across treatment conditions, we will conduct appropriate data transformations. Where appropriate, we will use confirmatory factor analysis to construct and evaluate measurement models of key constructs prior to conducting hypothesis tests involving these measures.

Models for Hypothesis Testing. Because patients are nested with physicians, multi-level models (MLM) will be used to test hypotheses for Aims 1 and 2. We will use multi-level structural equation models (MSEM) to examine hypotheses for Aim 3.

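### The plan contradicts itself on whether an analysis row is a visit or a patient; if visits are rows, repeated visit-level secondary outcomes have no term for within-patient correlation

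*Combined protocol and SAP*

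**What the plan says.** **Visit as the row.** Power and Sample Size Estimates says that "the unit of analysis is the patient-physician visit and data from these visits will likely be more similar within physicians than between physicians". Hypothesis 1a fits its models to "outcomes assessed during or after each visit in which a trial was discussed".

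**Patient as the row.** Power and Sample Size Estimates also says that "the outcomes of both interventions will be modeled at the patient level in a single model". Models for Aim 1 says that outcomes and intervention coefficients "will be modeled at the patient level of the model (level-1); that is, they will be nested within physicians (level-2"). Both power calculations use 24 physicians with 9 patients each, which is one record per patient.

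**Clustering.** Models for Hypothesis Testing gives one reason for a multilevel model: "Because patients are nested with physicians, multi-level models (MLM) will be used to test hypotheses for Aims 1 and 2".

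**Repeated visits.** Under Study Design Overview, active participation lasts until "they receive a trial offer, or they have four interactions with their physician without receiving an offer", and stops earlier if the physician intervention begins or data collection ends. Time 2 says of patients without an offer: "They will continue to be tracked for up to a total of 4 visits or until the end of their participation". Patient questionnaires surround each recorded visit, physicians report after each visit, and raters score the recordings.

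No section gives a patient random effect, a third level, patient-clustered standard errors, or a rule choosing one visit per patient.

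**The concern.** An analyst cannot build the data set from this text without choosing between two incompatible row definitions. On the visit reading, a man with several visits at which a trial was discussed supplies several rows, and the model links them only through his physician. Physicians and raters record discussion and offer separately, so a discussion without an offer is possible and repeated qualifying rows can occur.

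The tested terms are all between-patient contrasts. Arm is randomised per patient. Phase is fixed per patient, because first-half patients stop when the physician intervention starts. Race is fixed. Positive within-patient correlation that the model ignores therefore makes the standard errors of these terms too small. At stake are the tests of Hypotheses 1a to 1c and the race interactions for the visit-level secondary outcomes. Patients who are not offered a trial would also tend to supply more rows and so carry more weight.

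**Working it through.** **1. The plan's own figure.** For continuous outcomes the plan states power above .90 with 24 physicians, 9 patients each, d = .50, effect-size variance .05, 5% of variance due to physicians and α = .05. Using a noncentral F(1, 23) with residual variance 1:

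λ = 24 × .50² / (.05 + 4/9) = 6 / .4944 = 12.13, power = .915.

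The figure reproduces with one record per patient. Counting 36 independent visits per physician would give more than .999, so the plan did not count visits as extra sample here. The binary figure of more than .99 does not reproduce (about .38 two-sided). Four independent visits per patient (864 records) give only .90 to .91, so visit counting does not explain it; that is a separate matter.

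**2. Which outcomes can repeat.**

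| Outcome | Rows per patient |
|---|---|
| Decision (primary), understanding of the offered trial, enrolment | In practice one, after the offer that ends follow-up |
| Trial offer | Zeros, then at most one offer, then stop |
| Perceived patient-centeredness, involvement, trust, team perceptions, active participation, physician patient-centeredness | One per analysed visit, at most four |

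**3. Size for the repeating outcomes.** Inputs not in the documents, so assumed: m analysed visits per patient and within-patient correlation r. The formulas are DE = 1 + (m − 1)r, model SE / true SE = 1/√DE, and true two-sided α = 2[1 − Φ(1.96/√DE)].

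| m | r | DE | SE ratio | α, formula | α, simulated |
|---|---|---|---|---|---|
| 1 | any | 1.0 | 1.00 | .050 | .052–.056 |
| 2 | .1 | 1.1 | .95 | .062 | .060 |
| 2 | .3 | 1.3 | .88 | .086 | .094 |
| 2 | .5 | 1.5 | .82 | .110 | .111 |
| 4 | .1 | 1.3 | .88 | .086 | .090 |
| 4 | .3 | 1.9 | .73 | .155 | .170 |
| 4 | .5 | 2.5 | .63 | .215 | .228 |

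The simulation used 24 physicians with 9 patients each, arm randomised within physician, physician variance .05, physician effects but no patient effect, and 3,000 runs. It tested the arm term; phase and race follow by the same argument, since they too are constant within a patient.

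For unequal m, DE = 1 + (E[m²]/E[m] − 1)r.
- If 20% of patients have two qualifying visits and the rest one: E[m] = 1.2, E[m²] = 1.6, and at r = .5 DE = 1 + (1.333 − 1)(.5) = 1.17, so α is about .07. At 10% it is about .06.
- If visits are spread evenly over one to four: E[m] = 2.5, E[m²] = 7.5, and at r = .5 DE = 2.0, so α is about .17 (simulated .182).

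**4. Trial offer.** Simulated with up to four visits, stopping at the first offer, visit order as covariate, no patient term, an assumed first-visit offer probability near .35 and no physician effect. Type I error was .047, .052, .042 and .049 at latent within-patient correlations of 0, .23, .50 and .66, with about 2.4 rows per patient. There was no inflation.

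**5. Power after the fix.** With the patient level modelled, effective records per physician are 9m / [1 + (m − 1)r]. At r = .5, m = 2 gives 18/1.5 = 12 and power .966; m = 4 gives 36/2.5 = 14.4 and power .984. With one record per patient, power remains .915.

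**The case against.** The strongest reply is that the plan never specifies a visit-row model. Level 1 is labelled the patient, the primary sample is described as 216 patients, and the visit sentence explains the choice of power software. This stands in part: treating visits as independent rows is an inference from one side of a contradiction. It does not remove the problem, because Hypothesis 1a, which is model specification, takes outcomes from each qualifying visit.

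A reader might infer that every standard error in the trial is too small, including that for the primary outcome. The documents do not support this: decision, understanding and enrolment follow the offer that ends participation. A reader might also count trial offer among the affected outcomes. Because follow-up stops at the first offer, its rows behave like a discrete-time first-event analysis, and the Control variables paragraph already adjusts for the number of previous interactions. That covariate is a fixed effect, however, and does not model within-patient correlation in the repeated measures.

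A single headline error rate such as 14% or 17% is also unsupported. It needs a distribution of discussed visits and a correlation that the documents do not give. Four rows is a ceiling, since only visits with a trial discussion qualify and an extra row needs a discussion without an offer.

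Aim 3 is expressly exploratory with its structure left open, so an effect on the mediation models cannot be shown from the text.

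**Conclusion.** The contradiction is real and should be resolved before analysis. The statistical consequence is conditional: if visits are rows, tests of Hypotheses 1a to 1c and the race interactions on the repeated visit-level secondary outcomes would be anticonservative. With assumed within-patient correlation of .1 to .5, two-sided type I error is about 5% at one row per patient, 6–11% at two and 9–22% at four by formula, with simulation in close agreement. If few patients have a second qualifying visit, the excess is one or two percentage points. The primary outcome, understanding and enrolment are largely unaffected, and trial offer is not materially inflated.

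**What to change.** - State the row unit for each outcome, and remove the general statement that the unit of analysis is the visit.
- For outcomes measured at more than one visit, add a random patient intercept (visits in patients in physicians), or use patient-clustered standard errors, or prespecify one index visit per patient.
- Use one row per patient for decision, understanding and enrolment.
- For trial offer, use either one row per patient (ever offered) or an explicit discrete-time first-offer model with visit order.

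The cost is plan wording, one extra variance term and somewhat wider standard errors for the repeated outcomes. No added sample is needed on this account: the stated power above .90 for continuous outcomes still holds on the plan's own inputs.

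### The sample size is justified partly by power for Aim 1 interactions, but no calculation covers Hypothesis 1c, and at the plan's own effect sizes its power is low

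*Combined protocol and SAP*

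**What the plan says.** All references are to the combined protocol and SAP.

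- **Aim of the sample size.** Power and Sample Size Estimates, speaking of Aim 1, says "we seek a sample size that gives us sufficient power to detect both the main effect of intervention and important interaction effects".
- **Primary outcome.** The calculation takes 216 patients spread evenly over 24 physicians, alpha and ICC both .05, and a null success rate of .25. The stated result is that "we are well powered to detect p_H of .35 ($b = 0.48$, odds-ratio = 1.61) with power > .99".
- **Continuous outcomes.** The inputs are "between-physicians variability in effect size (σ_{β}^2) of .05, 5% of variance in outcomes due to physicians" and the stated result is "a medium effect size (d) of .50, power to find effects exceeds .90".
- **Hypothesis 1c.** It is one of three hypotheses under Aim 1, all tested in one multilevel model per outcome. It is judged by the product of the two intervention indicators: "we expect a statistically significant positive coefficient for the interaction term". Models for Aim 1 gives the expected interplay of the two interventions as the reason for modelling them together.
- **What is called exploratory.** The plan applies that label to Aim 3, to the additional moderator analyses and to the interview analysis. It does not apply it to Hypothesis 1c.

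No interaction effect size, cell size or power figure is given for Hypothesis 1c.

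**The concern.** A patient-by-physician interaction is a difference of differences across four cells, so at a given sample size it is estimated much less precisely than a two-group difference. A calculation for 108 against 108 therefore says nothing direct about the product term, yet the sample size is presented as serving both.

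Hypothesis 1c carries the multilevel rationale of the study. If its power is low, a non-significant product term is the likely result even when the two interventions do reinforce each other. A reader who relies on the stated aim of the sample size would not know that.

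**Working it through.** **Inputs from the plan.** 216 analysed patients, as 24 physicians with 9 each; ICC .05; alpha .05; rates .25 and .35; d = .50; effect-size variance .05; 5% of outcome variance between physicians. Study Design Overview puts half the patient sample before and half after the physician intervention, and randomises patients within physician.

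**Assumptions, because the plan is silent.** 1:1 randomisation; the halves carry over to the 216, giving four cells of 54; two-sided testing; an interaction as large as the planned main effect (odds ratio 1.61, or d = .50).

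**Step 1: the plan's figure for continuous outcomes.** For a two-group contrast blocked by physician, with noncentral F on 1 and 23 df:

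λ = J·d² / (σ² + 4v/n) = 24 × .25 / (.05 + 4/9) = 12.13, power .915.

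With within-block variance v = .95 power is .927. The stated value above .90 reproduces, as a 108 against 108 contrast.

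**Step 2: the plan's figure for the primary outcome.** Log odds ratio = ln[(.35/.65)/(.25/.75)] = .480.

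SE = √[1/(108 × .25 × .75) + 1/(108 × .35 × .65)] = .300, ratio 1.60, power .36.

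Multiplying the variance by (1 − .05) for treatment within cluster gives SE .293 and power .37; on the risk-difference scale it is .38. A GEE simulation (24 × 9, 1,500 runs) gave .41. The stated value above .99 does not reproduce; .99 would need about 767 patients per arm.

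**Step 3: Hypothesis 1c, continuous outcomes.** The sampling variance of the product term is 4v/54 = 16v/216, four times the 4v/216 of the main effect.

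- With v = 1 and slope variance .05: variance = 16/216 + .05/24 = .0762, λ = .25/.0762 = 3.28, power .41 (F test).
- With v = .95, no slope variance and a normal approximation: SE = √.0704 = .265, ratio 1.88, power .47.
- One-sided, the range is about .55-.59.
- 80% power needs d of about .75-.81.

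**Step 4: Hypothesis 1c, primary outcome.** SE = √Σ[1/(54·p(1−p))] over the four cells.

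| Cells | SE | Power, two-sided | Power, one-sided |
|---|---|---|---|
| .25, .35, .35, .584 (both main effects present) | .581 | .131 | .206 |
| same, variance × .95 | .566 | .135 | .212 |
| .25, .25, .25, .35 (no main effects) | .615 | .122 | .194 |
| same, variance × .95 | .599 | .126 | .199 |

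GEE simulation gave .13-.15. Over the same scenarios, power at an interaction odds ratio of 5 is .74-.77, at 5.5 it is .78-.81 and at 6 it is .81-.85. So 80% power needs an odds ratio of about 5.5-6. For an interaction of 10 percentage points (cells .25, .25, .25, .35), 80% power would need about 4 × .79 × 7.85 / .10² ≈ 2,480 analysed patients, where .79 is the sum of p(1−p) over the four cells.

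**Step 5: the lower-order coefficients.** Hypotheses 1a and 1b are tested by dummy-coded indicators in the model that also holds the product term. With 0/1 coding, the patient-intervention coefficient is its effect before the physician intervention, a comparison of 54 with 54. Power for that coefficient is about .20-.21 at odds ratio 1.61 and about .68-.76 at d = .50. The two-group figures in Steps 1 and 2 describe the average effect, 108 against 108.

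**The case against.** - **The quoted sentence states a goal.** It gives no achieved power for Hypothesis 1c. This is correct: the defect is a claim without support, and no stated Hypothesis 1c figure is being shown wrong. But the goal is offered as the basis for the sample size, and the design does not meet it at the effect sizes the plan uses.
- **The interaction size is assumed.** This also stands, and every figure here is conditional on it. Power rises to about .41 at an interaction odds ratio of 2.7 and about .71 at 4.5. These are far larger than the plan's main effect of 1.61. A smaller interaction does worse: about .14 at d = .25.
- **Testing could be one-sided, since a positive coefficient is predicted.** Sidedness is not stated. One-sided power is still only about .19-.21 on the primary outcome and .55-.59 on continuous outcomes.
- **The stated main-effect power leaves room.** It does not reproduce. Even at face value, a main-effect power of exactly .99 implies only about .57 for an interaction of the same size.

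A reader might infer two stronger things. One is that the plan will treat a non-significant product term as proof of no synergy. The documents say only what would support Hypothesis 1c, so that reading is a risk and not a stated rule. The other is that the statement of being well powered for 2-way and 3-way interactions covers Hypothesis 1c. That statement is attached to Aim 2 and patient race, and this point does not rest on it.

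**Conclusion.** The concern holds as a lack of support for the Aim 1 interaction claim. Both calculations are two-group contrasts, and Hypothesis 1c, a formal hypothesis judged by significance, has none. Given the assumptions listed in the working, its power is about .12-.14 on the primary outcome and .41-.47 on continuous outcomes. The detectable sizes at 80% power do not depend on the equal-size assumption, and on the primary outcome they lie well beyond any effect the plan names. Unequal cells would lower power further.

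It would go too far to say that Hypothesis 1c simply has a power of .13, since the plan fixes no interaction size. The documents do not use the word confirmatory for this hypothesis either; they only refrain from calling it exploratory.

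**What to change.** **Power and Sample Size Estimates**

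- Remove the claim of sufficient power for the Aim 1 interaction.
- State the Hypothesis 1c power and the detectable sizes at 80% (odds ratio about 5.5-6; d about .75-.81), with the assumptions of equal cells of 54, two-sided .05, ICC .05 and, for the power figures, an interaction equal to the main effect.
- Do not keep the figure above .99 as the main-effect power. Recompute and restate it separately; the stated inputs give about .36-.41.
- Say that the two-group figures apply to the average effect, 108 against 108, and not to a 0/1 dummy-coded coefficient fitted beside the product term.

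**Hypothesis 1c**

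- Report the product term as an estimate with a 95% confidence interval, and state that a non-significant result is not evidence of no combined effect.

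**Cost.** Wording only, with no added patients or data. The stated power becomes less favourable.
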